## **Design and Outcomes**

This is a pragmatic superiority trial to examine the strengths and weaknesses of COPES asynchronous (IVR-CBT-CP) versus synchronous CBT-CP using three aims. Aim 1: Using a randomized pragmatic trial design in 764 VHA patients, we will determine whether COPES+UC is superior to synchronous CBT-CP+UC at 4 (primary endpoint), 6 and 12 months post-enrollment on: 1) A measure of pain functioning (the interference subscale of the Brief Pain Inventory (BPI)-primary outcome), 2) NRS pain intensity, catastrophizing, insomnia, depression, pain self-efficacy, and treatment satisfaction, treatment dose, and Patient Global Impression of Change (4 months only). Tertiary outcomes include patient engagement (a patient attending at least one session of CBT-CP or completing at least one treatment week of COPES), time to first treatment session, time to complete treatment, number of participants who complete all 10 treatment sessions (completion=yes/no). . and 3) health care use including emergency and urgent care, and pharmacological and non-pharmacological pain care.

Evaluate uptake, engagement, and variation in outcomes across groups where treatment disparities are possible (e.g., gender, race/ethnicity) and among patients with co-morbid alcohol and substance use disorders that have traditionally been excluded from trials of non-pharmacological interventions.

Aim 2: Evaluate the intervention delivery costs of COPES and conduct a budget impact analysis.

Aim 3: Conduct a process evaluation using the Consolidated Framework for Implementation Research (CFIR) and RE-AIM to guide our evaluation. We will:

3a. Conduct CFIR-guided interviews with the coordinating site's clinicians (VACHS) and study site clinicians and administrators to assess their experience with and views regarding the COPES and CBT-CP interventions

3b. Communicate ongoing implementation findings with participating sites and stakeholders.

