Resource Use. *Intervention Costs.* Therapists will use a log to record time spent in intervention-related activities for all treatment days. Therapists will record this information on the IVR system's therapist interface using an online calendar that has mandatory data fields for this information. We will regularly review completion of this field during monthly quality assurance monitoring with weekly checks in the first month of the treatment during the trial and the first month of any new therapist's tenure. A random sample of 20% of all treatment days will be used in the estimation of personnel costs. Time records will be combined with wage data from the VA Financial Management System to estimate intervention-specific personnel costs. Technology costs of the COPES IVR program include fixed costs (e.g., software development and computer maintenance) plus variable costs (e.g., minute costs for IVR calls). One-time fixed start-up costs will be reported separately. *VA Inpatient and Outpatient Service Use* data will be obtained from the Musculoskeletal Diagnoses Cohort (MSD), a project currently underway as part of the VA Connecticut Healthcare System's CREATE. The MSD is developing validated algorithms for using VA electronic health record data to identify utilization events, comorbid conditions, receipt of opioid medications, and pain screening results, for patients with pain-related diagnoses.

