Intensity of Service Use. As exploratory analyses, we will compare service utilization during the 12 months post-baseline by category (e.g., dose of opioid medication dispensed (continuous variable), number of PCP visits (count), non-opioid medication dispensed (binary), non-pharmacological pain care (binary), use of emergency department (binary) and urgent care (binary)) between groups using linear/generalized linear mixed models with an appropriate outcome distribution. We will also consider two-parts models for the opioid dose and PCP visits outcomes in case of zero-inflation. We will conduct a budget impact analysis and will include the cost of the intervention (personnel, supplies, CBT therapist training, and IVR fixed/variable costs) as well as costs for specific medical care services likely to be affected. Data from CBT therapists time records will be combined with wage data from the VA Financial Management System to produce estimates of intervention-specific personnel costs. Costs associated with the use of specific medical care services, such as medications, will be obtained from the VA Managerial Cost Accounting (MCA) System. Cost analysis will be conducted in accordance with the guidance provided by Sullivan et al. including the use of sensitivity analysis and scenarios that allow for varying assumptions about intervention uptake, compliance or component costs. All resource use and cost comparisons will be adjusted for any observed differences in baseline characteristics. Because costs of resource utilization are usually skewed, alternative modeling techniques (e.g., log-transformed costs, negative binomial regression)

will be used. Information on non-VA care will be collected by automated IVR call assessment. To mitigate recall bias, we will use a two-time frame method that asks about utilization over the past 6 months and over the past 2 months with more weight given to the shorter timeframe.

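### If the log-cost option in Section 9.6 is used, the service-cost comparison estimates geometric rather than arithmetic means, with no retransformation and no rule for zero costs

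*Combined protocol and SAP*

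**What the plan says.** The Précis (Design and Outcomes) sets the economic aim: "Aim 2: Evaluate the intervention delivery costs of COPES and conduct a budget impact analysis".

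Section 9.6 carries it out in two paragraphs.

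- **Resource Use** builds delivery cost from the bottom up: "Time records will be combined with wage data from the VA Financial Management System to estimate intervention-specific personnel costs". Fixed and variable technology costs are added. No regression is mentioned.
- **Intensity of Service Use** first describes exploratory comparisons of utilisation over 12 months. On zeros it says: "We will also consider two-parts models for the opioid dose and PCP visits outcomes in case of zero-inflation". It then commits to the budget impact analysis ("We will conduct a budget impact analysis"), which covers the intervention and the medical services likely to be affected. Service costs come from the VA managerial cost accounting system. The analysis is to follow cited guidance, "including the use of sensitivity analysis and scenarios that allow for varying assumptions about intervention uptake, compliance or component costs".

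On the between-arm comparisons, the same paragraph says: "All resource use and cost comparisons will be adjusted for any observed differences in baseline characteristics". The sentence at issue comes next: "Because costs of resource utilization are usually skewed, alternative modeling techniques (e.g., log-transformed costs, negative binomial regression" are the techniques that will be used.

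The section does not state which of the two methods applies, what quantity is to be estimated, how a log-scale result would be returned to dollars, or what happens to a patient with zero cost.

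**The concern.** A payer's budget is the number of patients times the arithmetic mean cost per patient. A linear model on log cost compares mean log costs, so its exponentiated treatment coefficient is a ratio of geometric means. That is a different quantity when log-scale spread differs by arm.

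The logarithm of zero does not exist. The plan analyses emergency department use, urgent care use and some forms of pain care as yes/no variables, so it allows for non-users, and a non-user has zero cost in that category. Such patients must be dropped or given an arbitrary added constant, and the plan fixes neither.

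The two example methods also answer different questions. With no stated target or selection rule, the direction of the reported cost difference could depend on which one the analyst picks.

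**Working it through.** The plan states no cost mean, SD, log-scale SD or share of zeros, so it has no figure to reproduce. **Every cost distribution below is assumed.** The only input from the plan is 382 per arm (Section 9.2).

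**1. Level.** For log-normal cost with log-SD s, geometric mean / arithmetic mean = exp(−s²/2).

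- s = 0.5: 0.88
- s = 1.0: 0.61
- s = 1.5: 0.32
- s = 2.0: 0.14

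Exponentiating a mean log cost without correction would therefore understate the mean by 39% at s = 1.0 and by 68% at s = 1.5.

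**2. Ratio, no zeros.** Let s₁ and s₀ be the log-SDs in the numerator and denominator arms. Then arithmetic ratio = geometric ratio × exp((s₁² − s₀²)/2).

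| s₀ | s₁ | Factor | Geometric ratio | Arithmetic ratio |
|---|---|---|---|---|
| 1.0 | 1.0 | exp(0) = 1.00 | 0.80 | 0.80 |
| 1.5 | 1.5 | exp(0) = 1.00 | 0.80 | 0.80 |
| 1.0 | 1.2 | exp(0.22) = 1.246 | 0.80 | 1.00 |
| 1.2 | 1.5 | exp(0.405) = 1.499 | 0.80 | 1.20 |
| 1.5 | 1.2 | exp(−0.405) = 0.667 | 1.20 | 0.80 |

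With equal spread the ratios agree exactly. With 1.2 against 1.5 the direction reverses.

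**3. Test at equal arithmetic means.** The log-scale difference is then (s₁² − s₀²)/2 in absolute value, with standard error √((s₀² + s₁²)/382).

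- For 1.0 and 1.2: 0.22 / √(2.44/382) = 0.22/0.080 = 2.75. A two-sided 5% test rejects with probability of about Φ(2.75 − 1.96) = 79%.
- For 1.2 and 1.4: 0.26/0.094 = 2.76, again about 79%.

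**4. Zeros.** Take log-SD 1.2 in both arms, log-means of 8.0 (denominator) and 8.2 (numerator), and zeros in 10% and 20%.

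- Arithmetic ratio: (0.8/0.9) × exp(0.2) = 1.09.
- Exponentiated difference in mean log(cost + c), by simulation: 0.53 for c = 1, 0.66 for c = 10, 0.83 for c = 100.
- Hand check at c = 1, where a zero contributes log 1 = 0: exp(0.8 × 8.2 − 0.9 × 8.0) = exp(−0.64) = 0.53.

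The result lies on the wrong side of 1 and moves with a constant that the plan does not set.

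**5. The other named method.** A negative binomial model with log link and treatment as the only term was fitted to simulated costs, 382 per arm, 155 of the 764 values being zero. Its exponentiated coefficient was 1.434, and the ratio of sample arithmetic means was 1.434. This option targets the arithmetic mean and accepts zeros.

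**The case against.** The strongest case on the other side has four parts.

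- **Log cost is only an example.** It is one of two methods offered, and step 5 shows that the other has neither defect. A reader might infer that the plan commits to log costs, but the wording does not support that. What stands is that the plan permits them and gives no rule for choosing.
- **The link to the budget figure is not documented.** A reader might infer that the budget impact result will be too low or point the wrong way. No sentence feeds a regression estimate or a back-transformed log mean into that analysis. The skewness sentence follows the one on adjusted comparisons and most naturally covers those. The understatement in step 1 also requires uncorrected exponentiation, and the plan is silent on retransformation rather than prescribing that. Delivery cost lies outside the problem altogether.
- **Unequal spread is not shown.** Central delivery of COPES against locally varied synchronous care makes it conceivable. However, the standardisation described concerns therapist training, scripts and fidelity, while service costs arise from usual pain care that continues in both arms (Section 5.3.1). Likewise, two-part models are a contingency for two utilisation outcomes, not a forecast of zero costs.
- **The cited budget guidance may settle the target quantity.** This cannot be judged from the documents. As described in Section 9.6, its scenarios vary uptake, compliance and component costs, and none of these defines what the cost model estimates.

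These points narrow the concern. They do not remove it, because one of the two named methods targets the wrong quantity for a budget question and nothing in the plan corrects for that.

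**Conclusion.** The concern holds conditionally. If log-transformed costs are chosen, the adjusted between-arm comparison of service costs estimates a geometric mean ratio and has no defined treatment of zeros. Whether this misleads depends on differences between arms in log-scale spread or in the share of zeros. Under the assumed values the discrepancy ranges from none (equal spread, no zeros) to a reversal of direction. The documents supply no data to place the trial within that range.

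The reach is limited to service-cost comparisons that sit beside a secondary aim. The primary outcome is untouched. The change should be made before costs are analysed, because afterwards the choice between two methods that can disagree in direction would be open to question.

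**What to change.** In Section 9.6, Intensity of Service Use:

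1. Name arithmetic mean cost per patient, and its difference between arms, as the target.
2. Drop log-transformed costs, or keep them only as a sensitivity analysis with retransformation to dollars. The retransformation should be arm-specific, because a factor common to both arms cancels from the ratio and leaves it geometric.
3. Model cost on the dollar scale with a log-link generalised linear model that accepts zeros (negative binomial or quasi-likelihood). Where zeros are common, use a two-part model with a gamma second part; a gamma model alone cannot take zeros.
4. Report mean cost per arm and the mean difference, standardised over the trial sample, with bootstrap confidence intervals.
5. State that these means are used wherever the budget impact analysis takes service costs from the trial.

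The cost is a few sentences in the analysis plan and slightly more programming. Intervals for arithmetic means may be wider than those for geometric means.

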## **10. DATA COLLECTION AND QUALITY ASSURANCE**

### **10.1 Data Collection Forms**

The investigators are responsible for ensuring the accuracy, completeness, legibility, and timeliness of the data reported. The investigators will maintain adequate data collection mechanisms including electronically captured patient reported data from the study IVR system, approved data taken from the VA electronic health record via electronic download, and data taken from the live telephone electronic screening that is placed directly into a study database (no hand-written information is collected).

The following data will be collected from the patient electronic health record by the study data manager using the VA approved VINCI interface: demographic data, clinic visits, pain treatment, prescribed opioid and non-opioid pain

medications, and ICD-10 musculoskeletal diagnosis codes. These data will remain behind the VA firewall. These data are downloaded by VINCI staff based on data requests and provided to study staff via the VINCI interface located behind the VA firewall.

Study staff will collect information about patient engagement/adherence/completion/treatment quality for both study interventions. We will track participant adherence (time to treatment, engagement, dose, time to completion and treatment completion (yes/no). Engagement and adherence will be identified for COPES (IVR CBT-CP) patients by measuring number of calls answered on the telephone system and in synchronous CBT-CP through examining number of sessions attended in the electronic health record. For workload credit and co-payment billing purposes all sessions are recorded in the VA electronic health record. Study staff will collect session attendance and treatment format data at the same time as they do the post-treatment chart review for adverse events.

A live telephone screening call will be done with participants by research staff to confirm eligibility and some demographics. We will collect information on pain, current medical treatments being used for pain, ability to walk and balance, if the patient has a foot ulcer, the availability of a telephone to participate, if patient is undergoing detox in an inpatient unit for alcohol or substance abuse or psychiatric condition, or any other medical conditions that may impair the patient's ability to participate, sensory deficits that could interfere with participation, use of non-steroidal anti-inflammatory drugs (NSAIDs) for pain, address, race/ethnicity, gender, and marital status will be collected by patient report.

Study staff are not blinded. However, collection of this information occurs prior to randomization and the randomization allocation will be concealed. These data will be entered as it is collected directly into the study database which will be held behind the VA firewall.

Most data and outcome measures will be collected from patients via our automated IVR system. Participants randomized to the IVR-COPES arm will make daily reports of their pain intensity, pain interference, sleep, steps, skill practice, and self-efficacy as described in section 6.2 Description of Evaluation. Participants in both conditions will complete the study baseline, post-treatment, and follow-up assessment measures using the IVR system. Outcome measures are described in section 6.2 Description of Evaluation. IVR data are held in the IVR system and can be viewed by approved research personnel with a web portal, and then transferred to the VA through approved methods. For patients who do not adhere to the IVR system calls for data collection, we will mail surveys or offer to collect the survey information using a real-time telephone interview with study

staff. Survey data will then be entered into the study database behind the VA firewall by blinded study staff. Paper surveys will be kept in locked filing cabinets in the office of the research coordinator at VA Connecticut.

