Daily IVR assessment calls. Prior to treatment and after the study baseline evaluation, participants will undergo daily IVR assessment of pain intensity, pain interference, pedometer-measured step counts, sleep quality, and sleep duration for seven days to establish a baseline of function. After the baseline period, participants will continue to receive daily calls for the duration of the 10-week treatment. During the treatment period two additional questions regarding pain skill practice and progress toward the weekly meaningful activity goal will be included. Patient-reported data collected on the IVR assessment calls will form the basis for therapist feedback. Calls will continue through an immediate one-week post-treatment assessment period. COPES participants will receive automated calls each evening between 6pm and 10pm at a time pre-selected by the patient to ensure that each call captures the full 24-hour reporting period. On evenings when participants miss their scheduled call, the IVR system will call again 2 additional times. Alternatively, participants may initiate a call into the system themselves. Study staff automatically receive alerts when participants do not respond to their first call or do not respond to two consecutive daily calls. During the IVR call, participants may directly access the VHA suicide crisis line by press 777# from the main menu or leave a message for their COPES therapist.

Pedometer-Assisted Graduated Walking Program. The COPES intervention includes a graduated walking component supported by daily reporting of pedometer-measured step counts. Participants will report their daily step count during the daily IVR assessment. Each week, a new daily step target will be calculated by adding 10% to

the prior week's average daily step count and that target will be communicated to participants during the weekly personalized, asynchronous therapist feedback.

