## 5.4 Engagement, Adherence, and Completion Assessment

We will track time to treatment, dose, engagement (did the participants begin treatment) as well as adherence (how many sessions did the participant attend), time to complete treatment, and completion (attend all 10 treatment sessions/weeks yes/no).

**Engagement.** Because the most frequent drop out point in our prior trials has been after randomization, but prior to attending any treatment sessions, we will track participant engagement (did the participant begin treatment). Patient engagement will be defined as a patient attending at least one session of CBT-CP or completing at least one treatment week of COPEs.

**Dose.** We will track participant adherence (number of weeks engaged in IVR-CBT and number of sessions attended in in-person CBT-CP).

**Completion.** We will identify the number of participants who complete all 10 treatment sessions (completion=yes/no).

Engagement, adherence, and completion will be identified for COPEs (IVR CBT-CP) patients by measuring number of weeks that the participant was participating in COPEs (at least one call answered/week through the COPEs IVR system and in synchronous CBT-CP through examining number of treatment sessions attended as

documented by treatment notes in the electronic health record. For workload credit and co-payment billing purposes all synchronous sessions are recorded in the VA electronic health record. Study staff will collect session attendance and treatment format data at the same time that they do the post-treatment chart review for adverse events. We will perform subgroup analyses for the primary outcome and engagement.

Variable	Collection
Time to treatment from randomization (access- time to first treatment session)	Collected from electronic health record review by study RAs.
Number of treatment sessions received (burden- dose)	Number of sessions (weeks for IVR) attended
Engagement-Did participant complete one session	Collected from electronic health record review by study RAs using notes or CPT codes
Time taken to finish treatment	Number of days between randomization and last treatment session
Fidelity / quality assurance	Treatment quality checklist for both conditions. Assess presence of pain coping skill teaching, treatment session length (synchronous) skill practice, homework assignment and assessment of adherence to practice.
Treatment characteristics	Format (in-person, VVC, Skype) and mode (individual/group)

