Sensitivity Analyses. If there is heterogeneity in therapist-specific time trends, then our primary analysis may have an inflated Type 1 error rate. As a first sensitivity analysis, we will use the 4-month outcome as the dependent variable in a mixed model ANCOVA. The model will have fixed effects for treatment, site, gender, baseline BPI interference, and a therapist random effect. To deal with missing data, this analysis will be applied to multiple imputed datasets (see Missing Data Sensitivity Analyses section). We will check whether the conclusion from this analysis regarding the treatment effect is consistent with the conclusion from the primary analysis.

As a second sensitivity analysis, we will use a mixed model similar to the primary analysis model, except that time will be treated as continuous. We will check the linear time assumption by considering other polynomials (e.g. quadratic, cubic).

Secondary Analyses. We will use Holm's correction to adjust for multiple secondary analyses. We will also conduct a per protocol analysis as an adjunct to the ITT primary analysis defining a "dose" of treatment as having attended/answered calls for 3 treatment sessions.

IVR-collected data. Analysis of the continuous secondary outcomes collected by IVR (PEG-3, PHQ-8, Pain Catastrophizing Scale, Insomnia Severity Index, Pain Self-Efficacy Scale,) will be similar to the primary analysis. We will use a generalized mixed model for ordinal data to analyze the Patient Global Impression of Change outcome.

We will compare treatment dose (number of sessions, a count variable) and treatment satisfaction at 4 months (continuous) between groups by using a negative binomial generalized linear mixed model and linear mixed model, respectively. The models will include treatment, site and gender as fixed effects, and a random effect for therapist.

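### Section 10.1 counts COPES dose in answered calls where the rest of the plan counts weeks; if followed, it inflates a secondary outcome by up to 7-fold

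*Combined protocol and SAP*

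**What the plan says.** Most of the plan counts COPES exposure in weeks. Section 5.4 defines dose as weeks engaged for COPES and sessions attended for synchronous CBT-CP. Its variable table gives dose as "Number of sessions (weeks for IVR) attended", and it counts a COPES week when there was "at least one call answered/week". Section 10.3.5 repeats that rule. The monitoring indicators in section 9.4 use sessions/weeks for dose and set minimal dose at 3 sessions/weeks. Section 5.1 also gives COPES dose in weeks.

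Section 10.1 differs. It first says "We will track participant adherence (time to treatment, engagement, dose, time to completion and treatment completion (yes/no", which places dose inside adherence. It then says "Engagement and adherence will be identified for COPES (IVR CBT-CP) patients by measuring number of calls answered on the telephone system", and sets this against the number of sessions attended in the synchronous arm.

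Section 9.6 compares dose between arms with a negative binomial mixed model. It describes dose as a number of sessions and gives no COPES unit. The per-protocol rule there is "having attended/answered calls for 3 treatment sessions", which does not say whether the COPES unit is a call or a week.

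Section 5.1 schedules daily COPES calls for seven days before treatment and throughout the 10-week treatment, and adds: "Calls will continue through an immediate one-week post-treatment assessment period". No section says explicitly whether the calls before and after treatment count towards dose.

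The synchronous unit also varies. The précis and section 5.1 give synchronous dose as weeks engaged; section 5.4 gives it as sessions attended.

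**The concern.** Dose is a secondary outcome compared between arms, and the secondary analyses are Holm-adjusted. A higher COPES dose is also part of the rationale for superiority in sections 9.1 and 9.4. The comparison means something only if one unit in each arm stands for about the same amount of treatment. A week of COPES and a session of synchronous CBT-CP are matched by design, at 10 of each. A daily call and a session are not.

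A programmer deriving the variable from the data-collection section would count calls. The COPES dose, and with it the estimated rate ratio, would then be multiplied by the number of answered calls per counted week. A significant dose result could arise from the unit alone. Under Holm's step-down procedure, that rejection would also ease the threshold for the remaining secondary outcomes.

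**Working it through.** **No stated figure to reproduce.** The documents give no call-answer rate and no expected number of calls per week, so the size has to be bounded and then shown over assumed rates.

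**Inputs from the documents.** Seven scheduled calls per week for 10 weeks (section 5.1) give 7 × 10 = 70 calls. The weekly rule (section 5.4) gives at most 10 weeks. The synchronous course is 10 sessions (section 5.1).

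**Bound.** A counted week holds between 1 and 7 answered scheduled calls, so the ratio of calls to weeks lies between 1 and 7. This is a per-week bound, so the allowance of up to 14 weeks to finish treatment does not alter it.

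**Independent days (assumption).** With daily answer probability p, expected calls are 70p and expected counted weeks are 10 × [1 − (1 − p)^7]. The ratio is 7p / [1 − (1 − p)^7].

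| p | Calls | Weeks | Ratio |
|---|---|---|---|
| 0.1 | 7 | 5.22 | 1.3 |
| 0.3 | 21 | 9.18 | 2.3 |
| 0.5 | 35 | 9.92 | 3.5 |
| 0.7 | 49 | 10.0 | 4.9 |
| 0.9 | 63 | 10.0 | 6.3 |
| 1.0 | 70 | 10 | 7.0 |

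Here a 3-fold change needs p = 0.419 and a 5-fold change needs p = 0.714.

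**Patients who differ (assumption).** Let each patient's p follow a Beta distribution with mean 0.3, 0.5 or 0.7 and concentration 2. Mean calls are 21, 35 and 49; mean weeks are 6.8, 8.75 and 9.6. The ratios are 21/6.8 = 3.1, 35/8.75 = 4.0 and 49/9.6 = 5.1. With concentration 1 or 3 instead, the ratios over the same means ran from 2.9 to 5.4.

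**Effect on the comparison.** If mean synchronous sessions are S, the call-based ratio is (calls/S) = (weeks/S) × (calls/weeks). Arms with equal dose in weeks and sessions would show a dose ratio of 3.1 to 5.1 under the Beta assumption with concentration 2.

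**Engagement.** Within treatment weeks, at least one answered call and at least one week with an answered call are the same event. Agreement was 100% in simulation.

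**Three-unit threshold.** Three calls can fall in one week, so individuals can be classified differently. In simulation with concentration 1 or 3, the share reaching the threshold differed by about 1 percentage point or less; for example, 67.6% by calls and 66.7% by weeks at mean 0.3 and concentration 1.

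**Calls outside treatment.** Counting the pre-treatment and post-treatment weeks raises the maximum to 12. Under the Beta assumption with concentration 2, it adds 2 × 0.68 = 1.4 weeks at mean 0.3 and 2 × 0.96 = 1.9 weeks at mean 0.7. For scale, the dose difference in the prior efficacy trial was 2.3 weeks (95% CI 1.0 to 3.6; section 2.2).

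**The case against.** The strongest reply is that dose is already defined in weeks in sections 5.1, 5.4, 9.4 and 10.3.5, and that section 10.1 only names data sources: the telephone system for COPES and the health record for synchronous CBT-CP. Answered calls are the raw record from which counted weeks are derived. On this view nobody would set total calls against sessions.

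Much of this stands. Section 10.1 is the outlier, and the sponsor probably intends weeks. But its sentence states a measure, puts dose under it, and opposes it to sessions attended; section 9.6 does not settle the unit. The conflict is on the page.

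The reply also holds against several stronger readings that a reader might infer:

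- That engagement changes 3- to 5-fold. It is a yes/no variable and does not change within treatment weeks. It could differ only if calls before or after treatment were counted. That possibility has some substance, because section 5.4 says that the most frequent drop-out point in prior trials was after randomization and before any treatment session.
- That 3- to 5-fold is the plan's own figure. It rests on assumed answer rates; with independent days, a 30% rate gives only 2.3-fold.
- That the per-protocol set is materially altered. Section 9.4 already states the matching minimum as 3 sessions/weeks, and the share reaching three units barely moves.
- That COPES is bound to win on dose. This follows only if the 10.1 wording is used in place of the definitions elsewhere.

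On the extra call weeks, sections 5.4 and 9.6 speak of treatment weeks, which favours excluding them. An explicit statement is a refinement.

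**Conclusion.** The concern holds for the dose count. Section 10.1 states a unit for COPES adherence, dose included, that conflicts with 5.4, 9.4 and 10.3.5, and the analysis section leaves the unit open. If 10.1 were followed, the COPES dose count and the dose ratio against synchronous sessions would be inflated by up to 7-fold, the only limit that the documents supply. The narrower range of about 3 to 5 assumes mean answer rates of 30% to 70% with variation between patients.

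The primary outcome is untouched. The correction should be made before dose is compared between arms, because the conflict affects an outcome that supports the superiority rationale and is easy to remove.

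**What to change.** - Replace the sentence in 10.1, and state in 9.6, that COPES dose is the number of treatment weeks with at least one answered call, not counting the seven-day pre-treatment and one-week post-treatment call periods.
- Word the per-protocol rule in 9.6 as 3 treatment weeks (COPES) or 3 sessions (synchronous), matching the minimal dose in 9.4.
- Reconcile the précis and section 5.1, where synchronous dose is in weeks, with section 5.4, where it is in sessions.
- Report the number of calls answered descriptively, within COPES only.

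The cost is wording and one derivation rule. No new data are needed, since the weekly rule already relies on the call records in the IVR system. The downside for the sponsor is that the reported COPES dose will be less favourable than a call count.
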